- EBTs for smoking cessation will be operationalized as: 1) utilization of any EBT over the 7-month study period; 2) total number of EBTs utilization during the 7-month study period (ranging 0 to 4); 3) EBT utilization index score (UIS; obtained by first computing a proportion of utilization score for each of the EBTs for each participant, and then adding up the individual proportion scores; see section 9.4.1 for details); 4) combination of at least one form of non-pharmacologic EBT and at least one form of pharmacologic EBT over the 7-month study period.
- Quit smoking attempts (assessed at Time 4 – 6). The number of quitting smoking attempts participants have made, since last contact, that have lasted 24 hours or more and that were not due to hospitalization or illness.
- Motivation to quit smoking (assessed at Time 4 – 6). Participants' motivation to quit smoking within 30 days (yes vs no).
- Smoking abstinence (assessed at Time 4 – 6). Seven-day point-prevalence abstinence (7-day ppa) assessed by self-report of no smoking, not even a puff, in the past 7 days and salivary cotinine level < 15 ng/mL.
- Mediators of treatment effects (assessed at Time 2 – 6). Theoretically driven constructs hypothesized to mediate any observed intervention effect (EBT utilization, quit smoking attempts, motivation to quit, or smoking abstinence) include the social cognitive theory constructs of motivation, self-efficacy, and outcome expectancies.
- Moderators or treatment effects (assessed at baseline). Moderating factors include sex, race or ethnicity, perceived stress and readiness to quit smoking.

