#### Secondary Endpoints:

We hypothesize that, compared to smokers who receive the Control intervention, smokers who receive the Intervention will:

- a) have more quit attempts during the 7-month study period (Aim 2 Hypothesis 2.1)
- b) have higher motivation to quit at 1-month post-appointment and 3- and 6-months follow-up (Aim 2 Hypothesis 2.2)
- c) have greater biochemically verified abstinence rates at 1-month post-appointment and 3 and 6 months follow-up (Aim 3 Hypothesis 3.1)

Alternatively, our null hypotheses are that there will be no difference between the two study groups on these secondary endpoints.

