Aim 2. Quit attempts and motivation to quit, and Aim 3. Biochemically verified abstinence. Dichotomous data on quit attempts, motivation to quit, and biochemically verified abstinence will be collected at one-month post-appointment (the end of the text message program), and at 3 and 6 months follow-up. Data on quit attempts will be based on the question "Since last contact, how many times have you stopped smoking for at least 24 hours because you were trying to quit smoking (not due to illness/hospitalization)?" Our main analyses for this outcome will examine the dichotomized outcome of 'any quit attempt', although we will collect data on the number of attempts and duration. Motivation to quit will be based on the question "Are you seriously thinking of quitting smoking in the next 30 days (yes or no)?" To determine point-prevalence abstinence, participants will be asked "In the last 7 days, have you smoked any cigarettes at all, even a puff?" For those responding 'no', biochemical verification will be implemented with salivary cotinine, with abstinence defined as cotinine values < 15 ng/mL. If participants indicate use of Nicotine Replacement Therapy or electronic nicotine delivery system use, these data will be recorded and reported separately from cotinine-validated abstinence. For these outcomes, the Intervention will be compared to the Control on data from 1-month post-appointment and at 3 and 6 month follow-up through mixed effect logistic regression models with random intercepts for longitudinal dichotomous data. These models will include indicator variables for intervention group, time, and interaction between intervention group and time (which will model and test whether changes in motivation to quit follows different patterns over time in the

Based on the NIH Behavioral and Social Intervention Clinical Trial Protocol Template v3.0 - 20180827

Intervention vs. Control group). Intervention effects will be described through odds ratios and 95% confidence intervals. In the case of significant intervention by time interaction, separate odds ratios will be given for intervention effects at each time point. We will control for age, gender, race/ethnicity, and variables identified through preliminary analyses as significantly differing between study groups.

---

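### Neither Hypothesis 2 endpoint has a sound scoring for participants who have already quit: sustained quitters count as non-attempters at Times 5 and 6, and the motivation item has no favourable answer for them

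*Combined protocol and SAP*

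**What the plan says.** **Quit attempts (Hypothesis 2.1).** Section 9.1 predicts that the Intervention group will "have more quit attempts during the 7-month study period". The item in Section 9.4.3 begins "Since last contact, how many times have you stopped smoking for at least 24 hours because you were trying to quit smoking". On the analysis, the section says: "Our main analyses for this outcome will examine the dichotomized outcome of 'any quit attempt', although we will collect data on the number of attempts". Duration of attempts is also collected.

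**Motivation (Hypothesis 2.2).** Section 9.1 predicts that the Intervention group will "have higher motivation to quit at 1-month post-appointment and 3- and 6-months follow-up". Section 8.1 defines the endpoint, assessed at Times 4 to 6, as "Participants' motivation to quit smoking within 30 days (yes vs no"), and the item in Section 9.4.3 reads "Are you seriously thinking of quitting smoking in the next 30 days (yes or no").

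**Model.** Section 9.4.3 puts both outcomes, with abstinence, into random-intercept logistic models over the 1-, 3- and 6-month assessments. Terms are group, time and their interaction, and if the interaction is significant an odds ratio is reported for each visit.

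**Abstinence.** Seven-day abstinence is asked at the same assessments and has its own hypothesis (3.1), which predicts a higher rate in the Intervention. Section 2.1 expects quit rates to be low but gives no figure. Sections 3, 8.1, 9.1, 9.3 and 9.4.3 contain no rule for scoring someone already abstinent on either Hypothesis 2 item.

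**The concern.** A good outcome in this trial is to quit early and stay quit. On the quit-attempt item that person truthfully reports a stop at the first assessment after quitting and none afterwards. In the per-visit model the record reads yes, then no, and from the second visit on it cannot be told apart from that of someone who made no attempt.

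On the motivation item the same person is asked about plans to do something already done. Coding the answer no counts abstainers against their arm. Leaving it blank limits the comparison to continuing smokers, a group formed after randomisation, which sits badly with the intention-to-treat principle of Section 9.3.

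If Hypothesis 3 is true and the Intervention has more sustained quitters, the attempt odds ratio is attenuated, and more so at later visits. The group-by-time term could then show an apparently fading effect that comes only from the scoring.

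**Working it through.** The plan states no rate, sample size or power for either Hypothesis 2 outcome, so there is no figure of its own to reproduce. All rates below are assumptions. The odds ratios are cross-sectional, one visit at a time; those from the random-intercept model will differ in size.

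OR = [p1/(1−p1)] / [p0/(1−p0)], with 1 = Intervention and 0 = Control.

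**1. Motivation.** Let a be the proportion abstinent and r the proportion ready among continuing smokers. The proportion scored favourable is:
- abstainers coded no: (1−a)r
- abstainers excluded: r
- abstainers credited: a + (1−a)r

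With a = 5% v 10% (Control v Intervention) and r = 50% in both arms:
- coded no: 0.475 v 0.450, OR = (0.450/0.550)/(0.475/0.525) = 0.90
- excluded: 0.500 v 0.500, OR = 1.00
- credited: 0.525 v 0.550, OR = (0.550/0.450)/(0.525/0.475) = 1.11

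Other assumed rates:

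| Ready among smokers | Abstinent | Coded no | Excluded | Credited |
|---|---|---|---|---|
| 50% v 50% | 3% v 6% | 0.94 | 1.00 | 1.06 |
| 50% v 50% | 10% v 20% | 0.81 | 1.00 | 1.23 |
| 40% v 50% | 3% v 6% | 1.40 | 1.50 | 1.57 |
| 40% v 50% | 5% v 10% | 1.33 | 1.50 | 1.62 |
| 40% v 50% | 10% v 20% | 1.19 | 1.50 | 1.76 |

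With equal abstinence the shift nearly vanishes. At 5% in both arms and 40% v 50% ready, coding no gives 0.380 v 0.475, OR = (0.475/0.525)/(0.380/0.620) = 1.48 against 1.50. With equal readiness as well, the OR is exactly 1.00.

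**2. Quit attempts.** Let q be the proportion already quit when an interval starts, n the proportion of the rest who make an attempt in it, and s the proportion of attempts that last. As planned, the visit scores (1−q)n. If the success is carried through abstinence, it scores q + (1−q)n. For the next interval, q becomes q + (1−q)ns.

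Take n = 30% v 40% and s = 10% v 15%. At Time 4, q = 0, because anyone reporting no smoking in the past 7 days at the appointment is terminated (Sections 5.4 and 8.1). This reads last contact at Time 4 as the appointment.

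| Visit | q | As planned | OR | Carried | OR |
|---|---|---|---|---|---|
| Time 4 | 0 v 0 | 0.300 v 0.400 | 1.56 | 0.300 v 0.400 | 1.56 |
| Time 5 | 0.030 v 0.060 | 0.291 v 0.376 | 1.47 | 0.321 v 0.436 | 1.64 |
| Time 6 | 0.059 v 0.116 | 0.282 v 0.353 | 1.39 | 0.341 v 0.470 | 1.71 |

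The attempt rates among those still smoking never change, yet the planned OR falls at each visit. With n = 30% in both arms and s = 10% v 20%, it runs 1.00, 0.96, 0.92.

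**3. Any attempt over 7 months.** This is 1−(1−n)³: 1−0.7³ = 0.657 v 1−0.6³ = 0.784, OR 1.89. Lasting attempts do not enter the formula, so no quitter is lost; with n = 30% in both arms the OR is 1.00 whatever s is. The 1.89 estimates a different quantity from the per-visit 1.56 and is not a corrected value of it.

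**The case against.** **The wording does not exclude all quitters.** A reader might infer that both items can be satisfied only by a current smoker. That is wrong for quit attempts: the look-back covers the interval, so a new quitter is a success at the first visit after stopping, and Time 4 is unaffected. This stands, and limits the attempt problem to sustained quitters at Times 5 and 6.

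**The handling on motivation is not stated.** A reader might infer that quitters are scored as failures or drop out of this endpoint. The documents state no coding, skip or exclusion rule, the questionnaires are not included, and Section 9.4.1 promises a formal SAP before unblinding. This also stands: the motivation defect is a missing rule. For attempts the defect follows from the stated item and model.

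**A penalty on the Intervention is not certain.** It requires the arms to differ in sustained abstinence, and excluding abstainers does not mechanically lower the odds ratio.

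**Misscoring and redefinition must be kept apart.** With 5% v 10% abstinent and 50% v 55% of smokers ready, the OR is (0.55/0.45)/(0.50/0.50) = 1.22 among smokers, 1.08 with abstainers coded no (0.475 v 0.495), and 1.33 as a composite (0.525 v 0.595). Only the step from 1.22 to 1.08 is misscoring; the step from 1.22 to 1.33 comes from crediting abstinence as motivation.

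**Interpretation is not lost.** A reader might conclude that a null Hypothesis 2 result could not be interpreted. That goes too far: abstinence and the number and duration of attempts are collected, so the result could be cross-tabulated afterwards. A rule chosen after unblinding would, however, be open to challenge.

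**Conclusion.** The point holds in limited form. For quit attempts, the per-visit variable does not match Hypothesis 2.1 and scores sustained quitters as non-attempters at Times 5 and 6. For motivation, abstainers have no valid favourable answer at any follow-up, and their scoring is unspecified.

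The size cannot be fixed from the documents. Under the assumed rates, with smokers equally ready, coding abstainers no gives a motivation OR between 0.94 and 0.81; the attempt OR falls from 1.56 at Time 4 to 1.39 at Time 6. These are illustrations, not bounds. At the low quit rates the protocol expects, the effect is modest, and with equal abstinence it is essentially absent. Hypothesis 2 is secondary, so the conclusion on use of evidence-based treatment is unaffected. The change should still be made, because it is a derivation rule that can be fixed before unblinding.

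**What to change.** In Section 9.4.3, and in the SAP before unblinding:

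1. **Quit attempts.** Analyse any 24-hour attempt over the 7 months as one cumulative variable, which matches Hypothesis 2.1. Alternatively, keep the per-visit model and score yes for a participant still abstinent on an attempt reported at an earlier visit. Define last contact, and state how a missed visit is handled.
2. **Motivation.** Define the endpoint at each visit, here and in Section 8.1, as abstinent for the past 7 days or ready to quit within 30 days. Tabulate the two parts by arm, and report the smokers-only comparison as a sensitivity analysis, noting that it conditions on a post-randomisation state.

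The cost is wording and a derivation; both rules use data already collected. The small downside is that motivation becomes a composite that overlaps with Hypothesis 3 and rests on self-reported abstinence, whereas the abstinence endpoint also requires cotinine below 15 ng/mL. Tabulating the parts keeps that visible.

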Text message content will focus on addressing myths about stop smoking medications, motivating contact with EBTs, re-emphasizing some of the concepts in the educational video, resolving ambivalence, information about EBTs and what to expect, and specific help to connect to an EBT. With regard to the latter, this will include embedded web links and phone numbers for the quitline, information about how to procure nicotine replacement at no cost, contact information for local smoking cessation clinics, and a direct opt-in link to the National Cancer Institute's text message program (SmokefreeTXT). Intervention text message content will be geared towards enhancing putative mediators (motivation, self-efficacy, outcome expectations). Text message engagement strategies include customization, tailoring, interactivity and polls/quizzes.

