#### 10.1.4 FUTURE USE OF STORED SPECIMENS AND DATA

This study will collect saliva sample(s) from participants for biochemical verification of smoking abstinence. This sample will be used to analyze the chemical cotinine, a by-product of nicotine found in the body that is used by many researchers to differentiate between smokers and non-smokers. No other tests or analyses will be performed on these saliva samples. We will store the saliva in a medical grade ultra-low-temperature freezer located at the Boston University medical campus and later ship to Salimetrics (Salimetrics® LLC; a leading company in saliva biomarker research) for cotinine analysis. The samples will only be identified with the study ID number. No identifiable information will be shared with Salimetrics, and no other test will be performed on the saliva samples either by us or other investigators. Samples will be destroyed according to Salimetrics's protocol after cotinine analysis.

We will store paper files in locked filing cabinets, and electronic files in computer systems with password protection and encryption. We will protect information by identifying all of the data we collect including saliva samples with a unique study ID number, which will only be linked to a name through a document kept securely locked at the study team office. Only study team members will have access to this document. The mastercode will be kept for 7 years after the end of the study to allow for reidentification for auditing purposes and in compliance with Boston University policy #FA-002.

---

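### The H3 abstinence endpoint needs cotinine below 15 ng/mL, but the plan does not say how self-reported quitters using NRT or e-cigarettes enter the model, and no sensitivity analysis covers it

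*Combined protocol and SAP*

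**What the plan says.** **Endpoint.** Section 8.1 defines abstinence as "self-report of no smoking, not even a puff, in the past 7 days and salivary cotinine level < 15 ng/mL". Section 9.4.3 agrees: for those who report no smoking, "biochemical verification will be implemented with salivary cotinine, with abstinence defined as cotinine values < 15 ng/mL". Sections 3 and 4.1 use the same threshold. None makes an exception for people taking nicotine in another form.

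**Nicotine users.** The only provision is in section 9.4.3, for participants who report such use: "Nicotine Replacement Therapy or electronic nicotine delivery system use, these data will be recorded and reported separately from cotinine-validated abstinence". Their status in the H3 model is not given.

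**The assay.** Section 10.1.4 describes "cotinine, a by-product of nicotine found in the body that is used by many researchers to differentiate between smokers and non-smokers", and states that nothing else will be tested in the saliva samples.

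**The arms.** Use of cessation medication, including NRT, at entry is an exclusion (section 5.2). Intervention texts include "information about how to procure nicotine replacement at no cost" (Synopsis; similarly section 6.1.1). Controls get the same brochure and assessment-only texts.

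**Analysis.** H3 uses a mixed-effects logistic model over the 1-, 3- and 6-month assessments, with a group-by-time term (section 9.4.3). The planned sensitivity analyses concern missing data only (sections 9.3 and 9.4.2).

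**The concern.** A person who has stopped smoking but is using NRT can have cotinine above the threshold and so fail the definition. Because users of cessation medication are excluded at entry, NRT use at follow-up arises after randomisation, and the Intervention is built to increase it. NRT also counts towards the primary endpoint of any evidence-based treatment. So if the Intervention succeeds on that endpoint partly through NRT, it could lose more of its true quitters from the H3 numerator than Control does.

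The plan leaves the coding open, and sections 4.1 and 6.3 list the statistician among those who know the allocation. A coding choice that moves the H3 odds ratio should be fixed before the data are seen by arm. At stake is the interpretation of a secondary hypothesis, not the primary one.

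**Working it through.** **1. The plan's own figures.** The documents give no expected abstinence rate, sample size or power for H3. The primary calculation (section 9.2) reproduces: 22.7% v 37.6%, 182 per arm (364/2), two-sided 0.05, gives power 0.875 (stated 0.87). The same two-proportion formula is used in step 3.

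**2. Formula.** Let pC and pI be true abstinence at one visit in Control and Intervention, and uC and uI the share of those true quitters using NRT at that visit. If NRT-using quitters count as non-abstinent, the observed rates are pC(1 − uC) and pI(1 − uI), and

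observed OR = odds[pI(1 − uI)] / odds[pC(1 − uC)], with odds(p) = p/(1 − p).

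Assumptions not in the documents:
- pC is 10%, varied from 5% to 15%.
- The true OR is 2.05, borrowed from the primary endpoint. At pC = 10% this gives pI = 18.55%.
- The u values are illustrative. The middle pair borrows the any-treatment rates in section 9.2 as a stand-in for NRT use among quitters.
- NRT users exceed 15 ng/mL.

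**3. NRT-using quitters counted as non-abstinent (true OR 2.05).**

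| uC / uI | Observed rates, pC = 10% | OR, pC = 10% | OR, pC = 5% to 15% |
|---|---|---|---|
| 5% / 8% | 9.5% v 17.1% | 1.96 | 1.97 to 1.95 |
| 22.7% / 37.6% | 7.7% v 11.6% | 1.56 | 1.61 to 1.52 |
| 30% / 50% | 7.0% v 9.3% | 1.36 | 1.41 to 1.31 |
| 22.7% / 22.7% (no arm difference) | 7.7% v 14.3% | 2.00 | 2.03 to 1.97 |

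Middle row at pC = 10%: 0.10 × 0.773 = 0.0773 and 0.1855 × 0.624 = 0.1158, so OR = (0.1158/0.8842)/(0.0773/0.9227) = 1.56. True quitters lost per 182: 182 × 0.10 × 0.227 = 4.1 in Control and 182 × 0.1855 × 0.376 = 12.7 in Intervention. Single-visit power falls from 0.65 to 0.24.

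**4. Other codings the sentence permits (22.7% / 37.6%, pC = 10%).**
- NRT-using quitters removed from numerator and denominator: OR 1.66.
- All NRT users removed, with NRT use equally common in quitters and non-quitters within each arm: OR 2.05, no bias.
- All NRT users removed, with non-quitters using half as much: OR 1.81.
- NRT-using quitters accepted on self-report: no loss from this source, but see step 6.

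**5. Timing.** Section 9.4.1 gives NRT a recommended length of 8 weeks (56 days). Assessments are at Day 30 (+21), Day 120 ± 21 and Day 210 ± 21. A course begun on Day 1 ends at about Day 57, after the first window and before the second opens (Day 120 − 21 = Day 99). The effect should therefore be greatest at month 1. It persists only if NRT is started late or prolonged, which is possible because Intervention reminder texts continue after week 4 (sections 4.3 and 6.1.1).

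**6. The opposite error.** Suppose there is no true effect (10% in each arm), 40% of Intervention and 20% of Control non-quitters use NRT, and 10% of those users wrongly report abstinence (all assumed). Accepting self-report gives 0.10 + 0.90 × 0.40 × 0.10 = 13.6% and 0.10 + 0.90 × 0.20 × 0.10 = 11.8%, OR 1.18.

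**The case against.** A reader might infer that the plan codes NRT users as failures, so that the H3 odds ratio is biased against the Intervention. The documents do not support that as a certainty. Separate reporting does not fix the model coding, and section 9.4.1 defers to a formal SAP still to be completed. The bias also needs higher NRT use among Intervention quitters at the visit itself, not just more NRT use over seven months. Section 9.4.3 refers to participants who report use, not only quitters. If all users are set aside and use is unrelated to quitting, the bias disappears (step 4). All of this stands and makes the point conditional.

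Two other inferences should be resisted. E-cigarettes are not among the promoted treatments, so nothing in the documents suggests that their use differs by arm. And replacing the endpoint with self-report in nicotine users would give up the verification that the protocol presents as a strength, and would admit the opposite bias (step 6).

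It is also fair to say that H3 is secondary and has no power calculation. None of this answers the gap itself: the coding is unstated, the literal definition fails anyone above 15 ng/mL, and no planned analysis shows how much that matters.

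**Conclusion.** The point holds as a gap in specification with a foreseeable direction. Under the literal definition, and if NRT use among true quitters is higher in the Intervention arm at a visit, the H3 odds ratio is understated. On the assumed inputs a true 2.05 becomes anything from 1.97 (negligible) to 1.31 (large), and 1.56 in the middle case. With equal NRT use it is almost unbiased (1.97 to 2.03). Month 1 is the visit most exposed.

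These are single-visit illustrations, not output of the planned mixed model. They rest on abstinence rates, NRT shares and an assay result in NRT users that the documents do not give. A reader might go further and conclude that a null effect will look like harm. The direction is possible under unequal NRT use, but the documents do not establish the inputs.

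**What to change.** 1. Keep cotinine-verified 7-day abstinence as the H3 endpoint.
2. State in the SAP, before unblinding, how self-reported abstainers who report NRT or e-cigarette use are coded in the H3 model at each visit: non-abstinent, abstinent, missing or excluded.
3. Prespecify one sensitivity analysis in the same mixed logistic model that accepts self-reported 7-day abstinence for participants reporting NRT or e-cigarette use and requires cotinine below 15 ng/mL for everyone else. Report it beside the strict analysis.
4. Report the number of such participants by arm and visit.
5. State that the two results will be read as a range for this source of misclassification, and that the H3 conclusion will be qualified if they disagree. They are not guaranteed bounds.

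Cost: SAP wording, one more model run and a small table. NRT and e-cigarette use is already to be recorded, and no new assay is needed. The drawback is that the sensitivity version is unverified in nicotine users and may over-count more in the Intervention arm, which is why it should accompany the strict analysis and not replace it.

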cessation video intervention via VR headset during teeth cleaning, 2) print materials about the EBTs, and 3) two text messages per day for 4-weeks and periodically throughout the study period to motivate engagement with EBTs; or Control group, consisting of: 1) relaxation video via the VR headset (to maintain provider masking) during teeth cleaning, 2) receipt of the same print materials about the EBTs as the Intervention group, and 3) assessment only text messages. Our primary outcome is contact with, and utilization of, EBTs. Secondary outcomes are quit attempts, biochemically verified point-prevalence abstinence from smoking, and motivation to quit. We will also assess mediators of the intervention effect (self-efficacy, motivation, outcome expectations) and moderators of intervention effects (e.g., gender, readiness to quit). Assessments will occur at baseline, immediately post-appointment, weekly during the 4-week text message program (via text message) and at follow-up (one-month post-appointment, and 3- and 6-months later).

Because we are proactively reaching patients, they may or may not be ready to quit smoking. Therefore, quit rates would be expected to be low if we were focusing on cessation, necessitating a very large sample to be able to compute power. The goal of the study is to test whether a clinic-based intervention that reduces provider burden and has minimal patient burden can drive patients to make contact with EBTs. Our prior research has shown that smokers who are not motivated to quit either lack knowledge about the EBTs, do not know how to access EBTs, and/or have myths about EBTs. The video-based intervention and subsequent four-week text message program addresses these barriers, and provides motivational strategies to make contact with EBTs.

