attempts and increase their motivation to quit; 2) To test the efficacy of the Intervention vs. Controls on biochemically verified smoking abstinence. Hypothesis 3 states: Participants in the Intervention will achieve higher rates of point-prevalence abstinence at follow-up; 3) To assess the mechanisms through which intervention effects occur (mediators such as self-efficacy, motivation, and outcome expectations) and to identify subpopulations for whom intervention effects differ (moderators such as gender and motivation to quit). Hypothesis 4 states: The Intervention will directly affect the putative mediators of intervention effect, which will in turn affect EBT engagement (contact) and utilization. The role of moderators will be exploratory.

Participants will be randomized (1:1) at the dental clinic, after receiving the study brochure and before watching the videos during their teeth cleaning. Randomization will be implemented by employing a stratified block procedure with small, random size blocks and will be stratified by motivation to quit (ready to quit smoking in 30 days vs. not ready to quit within 30 days). To avoid randomization errors, randomization will be configured within REDCap, the secure web application used to build and manage the questionnaires and study forms which is programmed and managed by the BU Biostatistics and Epidemiology Data Analytics Center (BEDAC). A biostatistician will build the randomization program. The study RA will trigger randomization by pressing the feature on the REDCap eCRF form using an iPad. All dental providers will be masked to treatment condition because both the Intervention group and the Control group will be watching a video through the VR headset. Only the PI, project director, statistician, and study RA who is in the clinic will be unmasked to treatment condition.

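### The quit-attempt, motivation and abstinence odds ratios will be subject-specific, further from 1 than the between-arm odds ratios that hypotheses 2 and 3 concern, and no between-arm effect estimate is planned

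*Combined protocol and SAP*

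**What the plan says.** Section 9.4.3 (Aims 2 and 3) collects three binary outcomes at 1 month after the appointment and at the 3- and 6-month follow-ups. It compares the arms by "mixed effect logistic regression models with random intercepts for longitudinal dichotomous data", with terms for arm, time and their interaction, adjusted for age, gender, race/ethnicity and any variables found to differ between arms. On the effect measure it says only "Intervention effects will be described through odds ratios and 95% confidence intervals". Visit-level results depend on the interaction test: "In the case of significant intervention by time interaction, separate odds ratios will be given for intervention effects at each time point".

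The hypotheses are about arms. Under Secondary Endpoints in section 9.1, the Intervention group will "have greater biochemically verified abstinence rates at 1-month post-appointment and 3 and 6 months follow-up", "have higher motivation to quit at 1-month post-appointment and 3- and 6-months follow-up" and "have more quit attempts during the 7-month study period". Section 4.1 words the abstinence hypothesis the same way: "Participants in the Intervention will achieve higher rates of point-prevalence abstinence at follow-up".

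No section says whether the odds ratio is meant as subject-specific or population-averaged. None plans a risk difference, a model-based rate by arm or a marginal odds ratio for these outcomes. Section 9.4.1 provides percentages as descriptive statistics and says that a formal SAP is still to be completed before unblinding.

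**The concern.** With a random intercept in a logistic model, the arm coefficient compares a participant in one arm with a participant in the other who has the same latent intercept and covariates. Averaging over the intercept pulls the odds ratio towards 1, so the two kinds of odds ratio agree only if the intercept variance is zero or the effect is null. Someone who reads an abstinence odds ratio of, say, 4.8 as a statement about quit rates will picture a larger gap between arms than the model implies.

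The plan would also print this figure under the same name as the odds ratios for any EBT use (section 9.4.2) and for combined counselling and medication (section 9.4.3). Those come from ordinary logistic regression with no random effect. What is at stake is how the secondary results are read, not whether they reach significance.

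**Working it through.** **The plan's own figure.** The documents state no power, rate or variance for hypotheses 2 and 3. The nearest figure is the primary power in section 9.2: 22.7% v 37.6%, 364 analysed (182 per arm), two-sided 0.05. With mean rate 0.3015:

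z = (0.149·√182 − 1.96·√(2·0.3015·0.6985)) / √(0.227·0.773 + 0.376·0.624) = (2.010 − 1.272)/0.640 = 1.15, which gives power 0.875.

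The stated value is 0.87, so it reproduces. The odds ratio from those rates is 2.05, as stated. This checks the inputs only and says nothing about hypotheses 2 and 3.

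**Assumed inputs (not in the documents).** Control and intervention rates p0 and p1, constant over visits. Within-person correlation φ of the binary outcome between visits, set at the control rate. Normal random intercept with SD σ.

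**Formulas**, with Z standard normal:
1. Rate in arm k: p_k = E[expit(b_k + σZ)].
2. Correlation: φ = (E[expit(b_0 + σZ)²] − p0²) / (p0(1 − p0)). Solve for σ.
3. Solve step 1 for b_0 and b_1. The conditional odds ratio is exp(b_1 − b_0).

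**One case in full.** Rates 5% v 10% give a between-arm odds ratio of (0.10/0.90)/(0.05/0.95) = 2.11. For φ = 0.5, σ = 3.91, b_0 = −7.090 and b_1 = −5.516. The conditional odds ratio is exp(1.574) = 4.83, and the ratio is 4.83/2.11 = 2.29.

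**Range of conditional odds ratios:**

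| φ | Abstinence 5% v 10% (between-arm 2.11) | Abstinence 8% v 14% (1.87) | Motivation 50% v 62% (1.63) |
|---|---|---|---|
| 0.1 | 2.34 | 2.04 | 1.72 |
| 0.2 | 2.64 | 2.24 | 1.84 |
| 0.3 | 3.05 | 2.53 | 2.01 |
| 0.4 | 3.70 | 2.97 | 2.25 |
| 0.5 | 4.83 | 3.70 | 2.65 |
| 0.6 | 7.17 | 5.15 | 3.38 |

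Divided by the between-arm value, these are factors of 1.06 to 1.45 for φ of 0.1 to 0.3, and 1.38 to 3.40 for φ of 0.4 to 0.6.

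**Cross-check by simulation.** Trials of 182 per arm with three visits were generated with carry-over of status between visits, and a common-effect random-intercept model was fitted. The four cases were abstinence 5% v 10% with 50% carry-over, the same with 70% carry-over, abstinence 8% v 14%, and motivation 50% v 62%. Median conditional odds ratios were 3.5, 6.9, 3.6 and 2.2, against population-averaged values of 2.1, 2.1, 1.9 and 1.6. The ratios are about 1.7, 3.3, 1.9 and 1.4. With equal rates of 8%, the test rejected in 4.2% of 120 simulated trials. These data did not come from a random-intercept model, so the gaps also contain some misspecification. They support the order of size only.

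**The case against.** The strongest defence is that a random-intercept logistic model is a standard choice for repeated binary data. Its odds ratio validly estimates a conditional target, and its interval is on the same scale. At any fixed intercept variance the conditional odds ratio is 1 exactly when the between-arm one is 1, so the test answers whether the arms differ. Observed percentages can be expected under section 9.4.1, and the coming SAP could name the target. All of that stands. But the percentages are unadjusted descriptives, and the effect estimate still would not be on the scale of the hypotheses.

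Several stronger readings are tempting but unsupported:

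- A reader might infer a factor of 2 to 4 as the expected size. The documents give no intercept variance or correlation. At a between-arm odds ratio near 2, such a factor needs σ of roughly 3 to 5, and with σ of 1 to 2 the factor is about 1.03 to 1.74.
- A reader might take "quit rates would be expected to be low if we were focusing on cessation" in section 2.1 to mean a large intercept variance. Rarity does not imply clustering. At φ = 0.5 and odds ratio 2.05, the factor is 2.03 to 2.21 for control rates from 5% to 50%. For quit attempts, each visit asks about a new interval, so persistence cannot be presumed.
- Calling it a within-person odds ratio is wrong, because arm does not vary within a person.
- The primary odds ratio in section 9.4.2 is not strictly a population odds ratio either, since it is conditional on covariates. The mixed model adds a further layer of conditioning.
- Whether the published odds ratios cited in the protocol are marginal or conditional cannot be judged from these documents.

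**Conclusion.** The point holds as a mismatch between the effect the plan will report and the effect its hypotheses describe. Unless the intercept variance is zero or the effect is null, the odds ratios for hypotheses 2 and 3 will lie further from 1 than the between-arm odds ratios. The plan neither says so nor supplies a between-arm estimate.

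Under the assumed rates, the gap is modest if outcomes are weakly correlated within a person, and can exceed threefold for abstinence at a correlation of 0.6. Which of these applies cannot be known from the documents. Nothing here shows an invalid test or calls for abandoning the mixed model. It is a cheap improvement to the reporting of secondary endpoints.

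**What to change.** Keep the mixed model for the hypothesis tests. In section 9.4.3 and the coming SAP, define the reported effect for any quit attempt, motivation to quit and verified abstinence as population-averaged. For each visit, whether or not the interaction is significant, give the model-standardised rate in each arm, the risk difference and the marginal odds ratio. Obtain these by averaging fitted probabilities over the estimated intercept distribution and the covariates, with bootstrap confidence intervals that resample participants. Label any mixed-model odds ratio as subject-specific wherever it appears, and report the estimated intercept SD beside it.

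The cost is some SAP wording and a little more programming, with no new data. The printed odds ratio will be smaller, and the standardised figures still rely on the assumed normal intercept distribution, which the SAP should state.
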